## Research Summary

### State your primary study objectives

**Aim 1:** Test whether PainPac is feasible (primary aim and outcome), low burden, engaging, and acceptable (secondary outcomes for primary aim).

**Hypothesis:** PainPac will have high feasibility (accrual [N=60]), attrition [<25%], adherence [>75%]), as well as low patient burden (physical, emotional, financial), high engagement (PainPac log in and coping skills practice >3 times/week), and high acceptability (>80% satisfaction) that is at least comparable to PCST-Video.

### State your secondary study objectives

**Aim 2:** Examine the impact of PainPac on pain severity, pain interference, pain self-efficacy, emotional distress, and quality of life (secondary outcomes for secondary aim).

**Hypothesis:** PainPac will demonstrate improvements in pain-related outcomes (e.g., self-efficacy, emotional distress) and quality of life for patients that are at least equivalent to the improvements experienced by PCST-Video participants.

**Aim 3:** Gather quantitative and qualitative post-treatment data on patients' preferences, confidence in using technology, barriers, and facilitators regarding PainPac to update and optimize PainPac for a future large randomized clinical effectiveness trial.

**Hypothesis:** This data will lead to optimization of PainPac to improve pain-related outcomes in cancer patients.

### Please select your research summary form:

Standard Research Summary Template

This is the regular (generic) research summary template which is required for all regular applications (unless your protocol fits under the other research summary templates in this category). Use of these instructions is helpful for ensuring that the research summary contains all necessary elements.

## Standard Research Summary

### Purpose of the Study

- Objectives & hypotheses to be tested

**Aim 1:** Test whether PainPac is feasible (primary aim and outcome), low burden, engaging, and acceptable (secondary outcomes for primary aim).

**Hypothesis:** PainPac will have high feasibility (accrual [N=60]), attrition [<25%], adherence [>75%]), as well as low patient burden (physical, emotional, financial), high engagement (PainPac log in and coping skills practice >3 times/week), and high acceptability (>80% satisfaction) that is at least comparable to PCST-Video.

**Aim 2:** Examine the impact of PainPac on pain severity, pain interference, pain self-efficacy, emotional distress, and quality of life (secondary outcomes for secondary aim).

**Hypothesis:** PainPac will demonstrate improvements in pain-related outcomes (e.g., self-efficacy, emotional distress) and quality of life for patients that are at least equivalent to the improvements experienced by PCST-Video participants.

**Aim 3:** Gather quantitative and qualitative post-treatment data on patients' preferences, confidence in using technology, barriers, and facilitators regarding PainPac to update and optimize PainPac for a future large randomized clinical effectiveness trial.

**Hypothesis:** This data will lead to optimization of PainPac to improve pain-related outcomes in cancer patients.

This work has the potential to create a paradigm shift for behavioral pain intervention practice. This project will be one of the first to demonstrate that a theory-based standalone mobile app (PainPac) with wide implementation potential is feasible and beneficial to cancer patients. PainPac may drastically increase the availability of behavioral pain interventions. PainPac may be particularly likely to benefit patients in low-resourced areas with no or limited access to trained behavioral pain specialists and patients unable to engage in interventions during business hours. If PainPac is feasible and shows promise for benefits, this work will result in a larger RCT (R01) optimizing and testing the effectiveness of PainPac.

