**Statistical Design and Analyses.** A pilot trial (N=60) will be used to compare PainPac (n=30) to PCST-Video (n=30) on measures of feasibility (primary aim), burden, acceptability, engagement, and initial pain-related outcomes. Sample size was informed by pilot trial guidelines for RCTs of behavioral interventions,  and past similar studies, that suggest 30 participants per condition is sufficient for determining feasibility and acceptability, and feasibility of a future definitive trial. We anticipate no more than 25% attrition by 1 month post- baseline, based on previous psychosocial studies with cancer patients. Both groups of 30 participants are needed because we aim to demonstrate two types of feasibility: feasibility of the PainPac app, which only requires the 30 PainPac participants, and feasibility of the subsequent larger RCT (i.e., recruitment, assessments), which requires all 60 PainPac and PCST-Video participants. We are recruiting both sexes and all genders, and we expect a nearly equal sample size between sexes. To account for sex as biological variable, we will describe all outcomes disaggregated by sex. We will examine intervention effects and use this data to optimize PainPac. Aim 1. Feasibility (accrual, attrition, adherence), burden, acceptability, and engagement will be assessed post-treatment and descriptive statistics will be produced for PainPac and PCST-Video. Overall trial feasibility benchmarks include reaching target accrual (N=60) within 15 months and <25% attrition by 1 month post- baseline. Descriptive statistics will be used to report non-eligibility and refusal. Data of non-completers will be compared to completers. 75% completed will serve as our feasibility benchmark. If >25% of consented patients drop out, PainPac will not be considered feasible. We do not expect attrition to be greater in the PainPac condition compared to PCST-Video. PainPac feasibility benchmarks include protocol adherence indicated by calculating the degree to which participants are willing/able to complete study assessments (pre, post, follow- up) and the 4 PainPac skills modules or 4 PCST-Video sessions. 75% completed will serve as our benchmark. If >25% of consented patients do not complete the intervention (modules /sessions and assessments), PainPac will not be considered feasible. We expect adherence in the PainPac condition will be at least comparable to PCST-Video. Patient Burden will be measured as a continuous variable by assessing physical, emotional, and financial burden of engaging in the study intervention. We expect burden will not be greater in PainPac compared to PCST-Video. Patient Engagement will be assessed by electronic app data (e.g., PainPac weekly log-ins) and patient self-report defined as the

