
number of times per week they practice the coping skills.  $\geq 3$  times/week will serve as the benchmark; if participants log into PainPac and/or practice the coping skills  $< 3$  times/week, PainPac will not be considered engaging. We expect engagement in PainPac will be at least comparable to PCST-Video. Acceptability will be indicated by 80% of patients reporting satisfaction with PainPac and PCST-Video ( $M=3.2/4$ ) on the CSQ. Aim 2. Between-group differences at follow-up will be characterized using Cohen's  $d$  and 95% confidence intervals. Consistent with recommendations for small pilot RCTs of behavioral interventions, we propose a conservative approach that focuses on describing effect size estimates and their variability instead of testing for significant group differences. As this is a small trial intended to provide signals the intervention is promising and data for a larger trial, all pre- to post-intervention and 1 month variables will be characterized using graphs/plots and descriptive statistics (e.g., mean, standard deviations, range). We will examine the pattern of findings to determine the best analytic plan for the subsequent trial. Pain may vary based on pain medications and disease stage/treatment; we will describe these variables and include them, when appropriate, as covariates in future larger trials. The subsequent trial will be fully powered to test two active conditions. Given our proposed sample size ( $N=60$ ), an a priori power calculation using G-Power suggests we will have  $>80\%$  power to detect medium-sized effects of  $d=0.74$  ( $\alpha=0.05$ , two-tailed). However, as noted above, our analytic plan focuses on describing between-group differences rather than testing for significant effects. Aim 3. We will use methods from applied thematic analysis to analyze interview data. First, we will create a codebook a priori that corresponds to major content areas from the interview guide. The codebook will include a coding matrix with categories, codes, and definitions. The analysts ([name] and a study member) will segment interview transcripts into major content areas using Nvivo and then use an inductive and iterative approach to identify data-driven codes. As new codes emerge, they will be applied to previously coded sections until all relevant information is captured. All codes will be grouped into themes and subthemes. The analysts will meet to discuss coding and resolve discrepancies in interpretation, and maintain an audit trail of coding and analytic decisions. The study team will review the qualitative findings and develop action steps for modifying the protocol. All data will be used to optimize PainPac for a large randomized clinical effectiveness trial. We will optimize areas related to patient preferences, barriers, beliefs, and cultural tailoring to increase usability and engagement and meet user needs.

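### The hypotheses claim PainPac is at least as good as PCST-Video, but no margin is set, Aim 1 has no between-arm interval, and 30 per arm cannot support the claim

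*Combined protocol and SAP*

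**What the plan says.** The hypotheses are comparative. For Aim 1, the primary objectives end with performance "that is at least comparable to PCST-Video", and Purpose of the Study repeats this, for example as "high acceptability (>80% satisfaction) that is at least comparable to PCST-Video". For Aim 2, the secondary objectives and Purpose of the Study expect improvements "that are at least equivalent to the improvements experienced by PCST-Video participants".

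Data Analysis & Statistical Considerations carries the claim forward as expectations. On adherence it says "We expect adherence in the PainPac condition will be at least comparable to PCST-Video". Engagement is treated in the same way, and attrition and burden are expected to be no greater with PainPac.

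The planned analysis is descriptive:

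- **Aim 1:** "descriptive statistics will be produced for PainPac and PCST-Video". The decision rules are absolute. For adherence, "75% completed will serve as our benchmark"; engagement has a benchmark of three times a week and acceptability one of 80% satisfied. No between-arm difference or interval is specified.
- **Aim 2:** "Between-group differences at follow-up will be characterized using Cohen's" d, with 95% confidence intervals. The stated approach is to describe effect sizes and their variability "instead of testing for significant group differences".
- **Power:** more than 80% for d=0.74, two-tailed alpha 0.05, N=60.

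Neither aim has a margin, or any statement of what result would confirm or refute comparability or equivalence.

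**The concern.** To say that one treatment is at least as good as another is to say that a deficit beyond some size has been ruled out. That needs a stated size and an interval to hold against it. Aim 2 has the interval but not the size; Aim 1 has neither. The power statement does not help, because power to detect a difference says nothing about ruling out a deficit.

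The absolute benchmarks do not fill the gap. They ask whether PainPac reaches a fixed level, not how it stands against PCST-Video, and both arms can pass while differing by an amount that matters.

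What is at stake is the wording of the conclusion. The pilot is meant to lead to a larger trial of an app that would remove the need for a therapist. With hypotheses phrased as they are, similar point estimates could be written up as confirming comparability and carried into that application without data that support it.

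**Working it through.** **Inputs from the plan:** 30 per arm, equal allocation; d=0.74, alpha 0.05 two-tailed, power above 80%; attrition of no more than 25%; completion benchmark 75%. Retention of 75% of 30 is 22.5, so 22 per arm is used as the low case.

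**Assumptions, because the plan gives no figures:** the illustrative completion counts, a true deficit of 0.4 SD, and the non-inferiority settings in step 5.

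**1. The plan's own figure.** Two-sample t-test, noncentrality d × sqrt(n/2) = 0.74 × sqrt(15) = 2.87 on 58 degrees of freedom. Power is 80.5%, so the stated figure reproduces. It applies to full enrolment; at 22 per arm it is 66.9%.

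**2. Precision for Aim 2.** Near d=0 the 95% half-width is 1.96 × sqrt(2/n).

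- n=30: 1.96 × sqrt(2/30) = 0.51
- n=22: 1.96 × sqrt(2/22) = 0.59

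An observed d of exactly zero would therefore leave a deficit of about half a standard deviation within the interval.

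**3. Precision for Aim 1 completion.** The smallest count that reaches 75% of 30 is 23 (76.7%). Wilson 95% limits are 0.591 to 0.882 for 23/30 and 0.744 to 0.965 for 27/30. The Newcombe interval for a difference combines these limits.

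- *23/30 in each arm:* difference 0; half-width sqrt((0.767 - 0.591)² + (0.882 - 0.767)²) = 0.21. Interval -21 to +21 points.
- *PainPac 23/30, PCST-Video 27/30:* difference 0.767 - 0.900 = -0.133.
  - Lower limit: -0.133 - sqrt((0.767 - 0.591)² + (0.965 - 0.900)²) = -0.32.
  - Upper limit: -0.133 + sqrt((0.882 - 0.767)² + (0.900 - 0.744)²) = +0.06.
  - Both arms pass the benchmark. The interval includes zero and also a deficit of 32 points.

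**4. How often an interval that includes zero would accompany a real deficit.** Suppose PainPac is truly 0.4 SD worse. The probability that the 95% CI includes zero is one minus the two-sided t-test power.

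- n=30: noncentrality 0.4 × sqrt(15) = 1.55; probability 67%
- n=22: noncentrality 0.4 × sqrt(11) = 1.33; probability 75%

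An interval that includes zero is thus no evidence of comparability at this size.

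**5. Whether adding a margin would rescue the claim.** For a one-sided 0.025 test, 80% power and no true difference, the smallest workable margin is (1.96 + 0.84) × sqrt(2/n).

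- n=30: 0.72 SD
- n=22: 0.84 SD

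A margin of 0.5 SD would need 2 × (1.96 + 0.84)² / 0.5² = 63 per arm, before allowing for dropout.

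**The case against.** The strongest reply is that this is a pilot which says openly that it describes effects and does not test them. Comparability in the analysis section is phrased as what the team expects, no decision is attached to it, and the subsequent trial is to be fully powered. All of that stands, and it limits the point. It does not remove it: the hypotheses still assert a comparative conclusion, and nowhere does the plan say that the pilot will refrain from drawing one.

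Two stronger readings are tempting, and the documents support neither.

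- **A reader might infer that the plan would pass a materially worse app as comparable.** No rule does this. The plan does not say that similar estimates, or an interval including zero, will count as support, and its go/no-go rules are absolute. Suppose true completion were 65% with PainPac against 80% with PCST-Video. The observed PainPac rate would be higher or at most 10 points lower in 38% of trials. Yet PainPac would reach 23/30 in only 12%, and would do both in 11%. If the 75% rule is applied to the PainPac arm, it stops most such apps.
- **A reader might infer that regression to the mean, from selecting on pain of at least 4 with no untreated arm, pushes both arms towards equivalent improvement.** Pain is re-assessed at enrolment, which reduces the effect. The planned Aim 2 contrast is between randomised arms, where regression common to both cancels in expectation.

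**Conclusion.** The point holds as a mismatch between hypothesis wording and analysis. No margin is stated for either aim, Aim 1 has no between-arm difference or interval, and the only power figure addresses a different question. With 30 per arm the pilot cannot establish comparability or equivalence at any margin tighter than about 0.7 SD with 80% power, and even identical completion in the two arms leaves 21 points of uncertainty each way.

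The effect is limited. Feasibility decisions do not depend on the comparison, Aim 2 already has 95% intervals, and significance testing is disclaimed. What remains is the risk of an unsupported comparability statement in the report or the next application. That is worth correcting because the correction is nearly free.

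The interval widths follow from the plan's sample size and attrition ceiling. The completion counts, the 0.4 SD deficit and the non-inferiority settings are illustrations. None of the figures is a reason to enlarge the pilot.

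**What to change.** - In both objectives statements, Purpose of the Study and Data Analysis & Statistical Considerations, replace the comparability and equivalence wording ("that is at least comparable to PCST-Video", "that are at least equivalent to the improvements experienced by PCST-Video participants" and the matching expectations) with an aim to estimate the difference from PCST-Video.
- Add one sentence stating that the pilot draws no comparability or equivalence conclusion.
- Report each Aim 1 between-arm difference with a 95% CI, using the Newcombe method for proportions, so that Aim 1 matches what Aim 2 already provides.

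The absolute benchmarks and the descriptive approach can stay as they are. The cost is a few extra intervals and a less favourable headline claim; no additional patients or data are needed.

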## Background & Significance

- Should support the scientific aims of the research

**SIGNIFICANCE.** Pain is one of the most common, interfering and distressing symptoms for patients with cancer. Pain has been identified as a significant problem that does not improve with time in cancer patients. A meta-analysis of studies (N=52) reported that more than half of patients with cancer report pain, with over 1/3 of patients reporting moderate to severe pain. Studies have routinely found that cancer patients report high levels of pain that are distressing and persistent across the cancer spectrum. Research has shown cancer patients with pain are more likely to experience psychological distress, physical disability, physical symptoms, lower quality of life, and increased financial difficulty than patients without pain.

Decades of work have shown behavioral pain interventions are efficacious for cancer-related pain. Teaching patients cognitive and behavioral strategies (i.e., relaxation, activity pacing, cognitive restructuring) for managing psychosocial factors related to pain can lead to decreased pain severity, increased pain coping self-efficacy, and decreased psychological distress. These interventions are traditionally delivered in person at a medical center by a trained masters or doctoral level behavioral pain specialists over 8-12 weekly sessions, all of which presents system, provider, and patient access barriers (e.g., availability, time, cost, burden). Our group and others have shown brief behavioral pain interventions (3-6 sessions) reduce pain and improve aspects of quality of life.

We have developed and tested numerous cognitive behavioral pain coping skills training protocols that enhance the abilities of patients with chronic disease to manage their pain, leading to improvements in pain and other important pain-related outcomes. Our group has extended this research by designing and testing pain coping skills protocols that use mobile health (mHealth) technology for cancer patients with pain. These protocols focus on decreasing patient burden and increasing patient accessibility and engagement by creating shorter protocols (4-6 sessions), using hybrid in person and videoconferencing methods, and using mHealth strategies (e.g., websites, smartphones, text messaging, real-time data collection with personalized feedback) to reduce intervention barriers (e.g., in person sessions). These mHealth pain coping skills interventions have shown high patient acceptability, feasibility, and efficacy. We published a large trial (N=178) showing a 4 session behavioral cancer pain intervention delivered with home-based videoconferencing is just as efficacious as a protocol delivered in person at the medical center. Importantly, the videoconferencing protocol showed significantly greater feasibility (i.e., attrition [16% vs. 30%], adherence) than the in person protocol.

Use of mHealth strategies and videoconference delivered behavioral pain interventions can improve patient access and decrease patient burden. However, videoconference delivered protocols retain some access barriers for many patients due to the therapist-led delivery model and resources required (e.g., expert pain therapist, scheduled appointments). Much more is needed to improve access for the greater than 22 million cancer survivors expected over the next 10 years. Developing additional behavioral approaches to cancer pain management is critical. A standalone behavioral cancer pain mobile application that uses efficacious cognitive and behavioral pain management strategies is likely to dramatically increase access to such interventions. A standalone app would eliminate the need for a therapist, be available to the patient at all times, and be easily accessible on a smartphone or tablet. Mobile apps also offer increased options for real-time personalization (e.g., messaging based on daily pain assessment) which can increase engagement and improve overall outcomes.

We have developed a mobile application – PainPac – that has been used only as an adjunct to in person and videoconferencing interventions. PainPac is a comprehensive mobile app program that provides patients four coping skills modules of efficacious cognitive-behavioral theory (CBT) based pain

management strategies (i.e., relaxation, activity pacing, cognitive restructuring). PainPac is a downloadable app available through iOS or Android. PainPac has been designed using information from three decades of research applying cognitive- behavioral pain management strategies to patients with chronic diseases including cancer. It uses Social Cognitive Theory to promote behaviors to improve self-efficacy for pain management and, in turn, improve pain and pain-related quality of life indices. PainPac's therapeutic elements are modeled after efficacious cognitive- behavioral interventions designed and tested by our group of behavioral pain experts (PI: [name], Co-I: [name], Mentor: [name]). Further, Drs. [name] and [name] completed a qualitative project with 33 national stakeholder interviews (e.g., policy makers, organization leaders, providers) that generated data to inform PainPac (see Preliminary Data); this is expected to improve our ability to generalize PainPac to settings outside of Duke. Importantly, PainPac's content is extended to patients in their daily life through interactive components like text messaging to improve skills engagement. Daily assessment of pain and skills practice will inform personalized messaging to further promote engagement. Finally, an engagement tool based on a reward system will be used for skills use engagement. We are currently using it as an adjunct to a videoconferencing intervention in two NIH funded trials (1R21CA235083, R01CA237892); we have not tested it as a standalone intervention.

PainPac is innovative as it is designed to be implemented through automated, electronic submission to patients via text, email, and/or MyChart when a patient reports pain at >4/10 at a clinical oncology appointment. PainPac has been carefully designed by our expert team of behavioral pain clinical scientists, a healthcare and research mobile app firm, and our institutional technology teams (see letter of support from [name], Chief Digital Strategy Officer at Duke). PainPac is expected to be beneficial to patients as a standalone intervention for the following reasons. PainPac has been designed to exploit three factors that, according to Social Cognitive Theory, strongly influence self-efficacy for pain control. First, PainPac enhances patients' mastery of pain coping skills by allowing them to access the intervention, practice skills, and receive encouragement on their own time, in their own environment, when they need it. Patients learn skills in short sessions (8 min) and receive daily prompts to apply the skills based on their symptom report (e.g., pain of 6/10 prompts a message to practice relaxation) – in this way patients are also getting what they need, not a static protocol. With traditional models, skill mastery can be difficult as patients are taught at the medical center and asked to go home and remember to practice, with assessment only at their next appointment and little personalization. Second, PainPac provides vicarious learning (i.e., modeling) experiences for each coping skill. Skills modeling takes place through videos and patient stories. Patients can access content any time via their smartphone; to increase salience of vicarious learning, the content has been targeted to cancer patients with pain. Third, patients will receive encouragement or corrective feedback personalized to their skills practice and symptom report (e.g., your pain is higher than normal, try practicing a skill that has worked for you in the past). These prompts are intended to provide feedback for patients that is psychoeducational and lends to a better mastery of self-management of pain.

A technology-based mobile application like we are proposing has the potential to drastically advance cancer patient behavioral pain management access. There is a time sensitive and critical need to optimize the impact of modern technology-based behavioral pain interventions to reach the growing number of cancer patients in the US. PainPac has been used only as an adjunct to our in person and videoconferencing interventions and the next step in this line of work is to test PainPac as a standalone intervention. This work could create a paradigm shift for behavioral pain intervention practice. If PainPac is feasible and acceptable to patients and shows promise for benefits, PainPac has the potential to drastically increase the availability of behavioral cancer pain interventions and lead to improved pain management for a greater number of cancer patients with pain.

